Appendix G. Dynamic International Prognostic Scoring System (DIPSS)

Table 14. Dynamic International Prognostic Scoring System (DIPSS)

	Points			
Prognostic Variable	0	1	2	
Age, years	≤ 65	> 65		
White blood cell count, × 10 ⁹ /L	≤ 25	≤ 25 > 25		
Hemoglobin, g/dL	≥ 10		< 10	
Peripheral blood blast, %	< 1	≥ 1		
Constitutional Symptoms*, Y/N	N	Y		
Risk Group	Points			
Low		0		
Intermediate-1 (INT-1)	1 or 2			
Intermediate-2 (INT-2)	3 or 4			
High		5 or 6		

^{*} To report constitutional symptoms as Yes, need presence of at least one of the 3 symptoms: weight loss, fever, or night sweats.

Notes: Passamonti F, 2010.²⁵

Table 15. Dynamic International Prognostic Scoring System (DIPSS)-PLUS

Prognostic Variable	Points			
	0	1	2	3
DIPSS Risk Score	Low-risk	Int-1	Int-2	High-risk
Platelet Count		$< 100 \times 10^{9}/L$		
Transfusion Need, Y/N	N	Y		
Unfavorable karyotype, ^a Y/N	N	Y		
Risk Group	Points			
Low	0			
Intermediate-1 (INT-1)	1			
Intermediate-2 (INT-2)	2 or 3			
High	4 to 6			

a. Unfavorable karyotype: complex karyotype defined as 3 or more abnormalities OR sole or two abnormalities that includes trisomy 8, 7/7q-, i(17q), 5/5q-. 12p-, inv(3), or 11q23 rearrangement.

Notes: Gangat N, 2011.²⁶

obbie Navitoclax (ABT-263)

M16-109 Protocol Amendment 11 EudraCT 2017-001398-17

Appendix H. Sample List of Excluded and Cautionary Medications

Anticoagulation Therapy (Excluded)

coumadin (Warfarin)^a and coumarin derivatives

e.g., phenprocoumon

fondaparinux (Arixtra)

heparin^b

melagatran/ximelagatran rivaroxaban (Xarelto)

apixaban (Eliquis)

Anti-Platelet (Excluded)

acetylsalicylic acid (Aspirin) (> 100 mg qd)

aspirin/extended-release dipyridamole (Aggrenox)

clopidogrel (Plavix)

dipyridamole (Persantine)

ticlopidine (Ticlid)

tirofiban (Aggrastat)

Strong CYP3A Inhibitors^c (Cautionary; Excluded for Cohort 1b DDI sub-study)

boceprevir nefazodone

clarithromycin nelfinavir paritaprevir/ritonavir

cobicistat posaconazole conivaptan ritonavir danoprevir/ritonavir saquinavir elvitegravir/ritonavir telaprevir idelalisib telithromycin tipranavir/ritonavir indinavir itraconazole troleandomycin ketoconazole voriconazole

lopinavir/ritonavir

mibefradil

SSRIs and SNRIs (Cautionary)

dalteparin (Fragmin) Enoxaparin (Lovenox) and other LMWH

Anticoagulation Therapy (Cautionary)

Tinzaparin (Innohep)

citalopram (Celexa) escitalopram (Lexapro) fluoxetine (Prozac) sertraline (Zoloft) duloxetine (Cymbalta)

vortioxetine (Trintellix) venlafaxine (Effexor) desvenlafaxine (Pristiq)

obbvie Navitoclax (ABT-263)

M16-109 Protocol Amendment 11 EudraCT 2017-001398-17

NSAIDS^a (Cautionary) CYP2C9 Substrates^c (Cautionary)

Aspirin > 100 mg daily fluvastatin Diclofenac glipizide Diflunisal irbesartan Etodolac losartan Ibuprofen phenytoin

Indomethacin sulfamethoxazole Ketoprofen sulfinpyrazone Nabumetone tolbutamide Naproxen torsemide

Oxaprozin Salsalate Sulindac Tolmetin

Strong CYP3A Inducers^c (Cautionary) CYP2C8 Substrates^{c, d}(Cautionary)

apalutamide amiodarone avasimibe amodiaquine carbamazepine (Tegretol®) cerivastatin enzalutamine chloroquine mitotane lovastatine

phenytoin (Dilantin®) paclitaxel (Taxol) rifampin (Rifadin®) pioglitazone St. John's wort repaglinide rosiglitazone

simvastatin (Zocor)e

troglitazone

P-gp Substrates (Cautionary)^c BCRP Substrates (Cautionary)c

dabigatran etexilate rosuvastatin digoxin sulfasalazine

fexofenadine

obbie Navitoclax (ABT-263)

M16-109 Protocol Amendment 11 EudraCT 2017-001398-17

P-gp Inhibitors (Cautionary)^c

BCRP Inhibitors (Cautionary)c

amiodarone carvedilol clarithromycin dronedarone itraconazole

lapatinib

curcumin cyclosporine A eltrombopag

[figure not shown]
lopinavir and ritonavir

propafenone quinidine ranolazine ritonavir saquinavir ritonavir telaprevir tipranavir ritonavir verapamil

P-gp Inducers (Cautionary)f BCRP Inducers (Cautionary)g

rifampin efavirenz phenytoin rifampin carbamazepine phenytoin St John's wort quercetin curcumin quercetin curcumin omeprazole imatinib

[figure not shown]
- Warfarin and certain NSAIDS are also CYP2C9 substrates. NSAIDS are allowed for limited duration only if platelets $> 100 \times 10^9/L$.
- Heparin may be used for patency of a central venous catheter and temporary use for prophylaxis of deep vein thrombosis.
- This is not an exhaustive list. For an updated list, see the following link http://www.fda.gov/Drugs/DevelopmentApprovalProcess/DevelopmentResources/DrugInteractionsLabeling/ucm0 93664 htm.
- Only certain statins qualify as CYP2C8 substrates.
- Significant increase in AUC by co-administration of gemfibrozile, a potent CYP2C8 inhibitor. However, the involvement of CYP2C8 is unclear.
- f. This is not an exhaustive list. Elmeliegy M, Vourvahis M, Guo C, et al. Clin Pharmacokinet. 2020;59(6):699-714.
- This is not an exhaustive list. Gameiro M, Silva R, Rocha-Pereira C, et al. Molecules. 2017;22(4):600. Refer to drug labels as needed for more information.

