 - Total Bilirubin ≤ 1.5 × ULN (exception: subjects with Gilbert's Syndrome may have a Bilirubin $> 1.5 \times ULN$)
 - Coagulation: aPTT and prothrombin time (PT) or INR $\leq 1.5 \times ULN$

Key Exclusion:

- Splenic irradiation within 6 months prior to Screening, or prior splenectomy
- Leukemic transformation (> 10% blasts in peripheral blood or bone marrow aspirate/ biopsy)
- Subject is currently on medications that interfere with coagulation (including warfarin) or platelet function within 3 days prior to the first dose of study drug or during the study treatment period with the exception of low dose aspirin (up to 100 mg/day) and low-molecular-weight heparin (LMWH).
- Prior therapy with a BH3 mimetic compound or stem cell transplantation

Diagnosis and Main Criteria for Inclusion/Exclusion (Continued):

Key Exclusion (Continued):

Cohort 1b Drug-Drug Interaction (DDI) sub-study subjects only: Subject has received strong CYP3A inhibitors (e.g., ketoconazole, clarithromycin) or moderate CYP3A inhibitors (e.g., fluconazole) within 14 days prior to the administration of the first dose of study drug.

Investigational Product: Navitoclax (ABT-263)

Cohort 1a Planned Dose(s): Dose Level –1: 25 mg once daily

Dose Level 1 (Starting Dose): 50 mg once daily

Dose Level 2: 100 mg once daily Dose Level 3: 200 mg once daily Dose Level 4: 300 mg once daily

Cohorts 1b, 2 and 3 Planned Dose(s) Dose Level –3: 25 mg once daily

Dose Level –2: 50 mg once daily

Dose Level –1: 100 mg once daily (Starting dose;

baseline platelet count $\leq 150 \times 10^9/L$)

Dose Level 1: 200 mg once daily (Starting dose;

baseline platelet count $> 150 \times 10^9/L$)

Dose Level 2: 300 mg once daily (after Week 24

for inadequate response)

Intermediate dose levels (e.g., 150 mg, once daily) may be considered for an individual subject at the discretion of the investigator. If intermediate dose levels are utilized prior to Week 24, consultation with the AbbVie TA MD/SD is required prior to implementation.

Mode of Administration: Oral

Reference Therapy: Ruxolitinib

 \geq 10 mg twice daily Dose(s):

Mode of Administration: Oral

Duration of Treatment: Until end of clinical benefit or occurrence of unacceptable toxicity or discontinuation criteria have been met.

Toxicity Management for Thrombocytopenia:

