 - Platelet count $\geq 100 \times 10^9 / L$ (Cohorts 1a, 1b or 3)
 - Platelet count $\geq 75 \times 10^9 / L$ (Cohort 2)
 - \circ ANC $> 1 \times 10^9/L$
 - Renal function: calculated creatinine clearance ≥ 30 mL/min using the Cockcroft-Gault formula
 - Hepatic function and enzymes:
 - \circ AST and ALT $\leq 3.0 \times$ upper normal limit (ULN)
 - \circ Total Bilirubin $< 1.5 \times ULN$ (exception: subjects with Gilbert's Syndrome may have a Bilirubin $> 1.5 \times ULN$)
 - Coagulation:
 - \circ aPTT $\leq 1.5 \times ULN$
 - Prothrombin time (PT) or INR $\leq 1.5 \times ULN$
- 16. Female subjects of childbearing potential must practice at least 1 protocolspecified method of birth control, that is effective from Study Day 1 through at least 30 days after the last dose of study drug.

If male, and subject is sexually active with female partner(s) of childbearing potential, he must agree, from Study Day 1 through at least 90 days after the last dose of study drug, to practice the protocol specified contraception (Section 5.2.5).

17. Females of childbearing potential must have a negative serum pregnancy test result at Screening, and a negative urine or serum pregnancy test on Study Day 1. Negative pregnancy test must be available prior to first dose.

Females of non-childbearing potential (as defined in Section 5.2.5) at Screening do not require pregnancy testing.

Rationale for Inclusion Criteria

- 1 In accordance with Harmonized Good Clinical Practice (GCP)
- 2 12, 14To select the subject population
- 13, 15 For the safety of the subjects
- 16 17The impact of the Navitoclax on pregnancy is unknown

5.2.2 **Exclusion Criteria**

A subject will not be eligible for study participation if he/she meets any of the following criteria:

- 1. Splenic irradiation within 6 months prior to Screening, or prior splenectomy.
- 2. Leukemic transformation (> 10% blasts in peripheral blood or bone marrow aspirate /biopsy).
- 3. Subject is currently on medications that interfere with coagulation (including warfarin) or platelet function within 3 days prior to the first dose of study drug or during the study treatment period with the exception of low dose aspirin (up to 100 mg/day) and LMWH.
- 4. Prior therapy with a BH3 mimetic compound or stem cell transplantation.

- 5. Subject has a history of an active malignancy other than MF within the past 2 years prior to study entry, with the exception of:
 - Adequately treated in situ carcinoma of the cervix uteri

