5.2.3 Enrollment of Subjects Based on Baseline Platelet Count

Cohort 1a only

Given the potential for navitoclax induced thrombocytopenia, the number of subjects with a baseline platelet count between $100 - 150 \times 10^9$ /L and $150 - 200 \times 10^9$ /L will initially be limited to approximately 6 - 8 subjects per platelet range, respectively. Data from at least the first 28 days of enrollment for approximately the first 6 subjects per platelet range enrolled in Cohort 1a will be reviewed by the TA MD/SD and Safety Physician. Upon review of these initial safety data, the sponsor will determine if further enrollment of patients within the specified platelet ranges should continue.

Cohort 2 only

Given the potential for navitoclax induced thrombocytopenia, the number of subjects with baseline platelet count between $75 - 100 \times 10^9$ /L will be limited to approximately 10 subjects. Data from at least the first 28 days of treatment for the first 5 to 6 subjects with lower platelets enrolled in Cohort 2 will be reviewed by the TA MD/SD and Safety Physician. Upon review of these initial safety data, the sponsor will determine if further enrollment of patients within the specified platelet ranges should continue.

5.2.4 **Prior and Concomitant Therapy**

Any medication or vaccine (including over-the-counter or prescription medicines, vitamins and/or herbal supplements) that the subject is receiving at the time of enrollment, or receives during the study, must be recorded along with the reason for use, date(s) of administration including start and end dates, and dosage information including dose, route and frequency.

Subject must not have received any live vaccine within 4 weeks prior to the first dose of study drug or be expected to need of live vaccination during study participation including at least 4 weeks after the last dose of study drug.

Best supportive care and treatment will be allowed for each subject (antiemetics, antibiotics, transfusions, nutritional support, pain control, etc.) with the exception of the following:

- Clopidogrel, tirofiban and other anticoagulants, drugs or herbal supplements that affect platelet. Administration of low-dose aspirin (≤ 100 mg daily) and LMWH are allowed; Dose adjustments for LMWH heparin should be made based on the subject's platelet counts and the local label of the agent being used.
- Disulfiram is not allowed during study drug treatment due to potential prolongation of prothrombin time (PT).

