A sample list of excluded medications and cautionary medications can be found in (Appendix H). Since a complete list of medications that are excluded or should only be used with caution cannot be provided, please refer to the appropriate product label and/or contact the AbbVie TA MD/SD whether a specific concomitant medication falls into the above mentioned categories. Information regarding potential drug interactions with navitoclax can also be located in the current navitoclax Investigator's Brochure.

If the investigator determines that use of an excluded or cautionary concomitant medication is medically indicated, the investigator will notify the AbbVie TA MD/SD and discuss the rationale for the use of the concomitant medication and the need to medically monitor the potential study subject under consideration.

Subjects Receiving Ruxolitinib

Ruxolitinib is predominantly metabolized by CYP3A4 and to a lesser extent by CYP2C9. For subjects who are taking strong CYP3A4 inhibitors (such as ketoconazole and clarithromycin) or moderate CYP3A4 inhibitors (such as fluconazole) concurrently with ruxolitinib study treatment, the local, approved product label should be referenced for ruxolitinib dose reduction, interruption, and discontinuation, or monitoring guidelines. The local, approved ruxolitinib product label should also be referenced for monitoring guidelines when co-administered with CYP3A inducers or drugs transported by P-gp and BCRP.

5.2.5 **Contraception Recommendations**

While participating in this research study, subjects should not become pregnant, breastfeed a baby or father a baby.

Contraception Requirements for Females

Subjects must follow the following contraceptive guidelines as specified:

Females, Non-Childbearing Potential

Females do not need to use birth control during or following study drug treatment if considered of non-childbearing potential due to meeting any of the following criteria:

- 1. Premenopausal female with permanent sterility or permanent infertility due to one of the following:
 - Permanent sterility due to a hysterectomy, bilateral salpingectomy, bilateral oophorectomy
 - Non-surgical permanent infertility due to Mullerian agenesis, androgen insensitivity, or gonadal dysgenesis; investigator discretion should be applied to determining study entry for these individuals.

2. Postmenopausal female

- Age > 55 years with no menses for 12 or more months without an alternative medical cause.

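### Appendix H of the protocol lists aspirin above 100 mg per day as both excluded and cautionary; the cautionary entry conflicts with exclusion criterion 3

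*Protocol*

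**What the plan says.** Appendix H of the protocol is a sample list of excluded and cautionary medications, and Section 5.2.4 refers sites to it. Aspirin above 100 mg per day appears in it twice:

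- Under the excluded anti-platelet heading: "acetylsalicylic acid (Aspirin) (> 100 mg qd").
- Under the cautionary NSAID heading: "Aspirin > 100 mg daily".

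The NSAID heading carries a footnote: "NSAIDS are allowed for limited duration only if platelets" are above 100 × 10⁹/L.

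Three other places set the aspirin rule:

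- Synopsis (Section 1.2), key exclusions: drugs that interfere with coagulation or platelet function are barred "with the exception of low dose aspirin (up to 100 mg/day) and low-molecular-weight heparin (LMWH").
- Section 5.2.2, exclusion criterion 3: the same bar applies within 3 days before the first dose or "during the study treatment period with the exception of low dose aspirin (up to 100 mg/day) and LMWH".
- Section 5.2.4, aspirin bullet: "Administration of low-dose aspirin (≤ 100 mg daily) and LMWH are allowed".

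Section 5.2.4 also has a bullet permitting NSAIDs for a limited time when platelets exceed 100 × 10⁹/L. It does not name aspirin.

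On the standing of the list, Section 5.2.4 says "Since a complete list of medications that are excluded or should only be used with caution cannot be provided". It adds that if "use of an excluded or cautionary concomitant medication is medically indicated, the investigator will notify the AbbVie TA MD/SD" and discuss the reasons.

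**The concern.** A site that looks up aspirin above 100 mg per day in Appendix H gets one of two answers, depending on which heading it reads. Under the anti-platelet heading the drug is barred. Under the NSAID heading, with its footnote, a short course is acceptable if platelets are above 100 × 10⁹/L. An exclusion criterion that runs through the treatment period forbids that second use.

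The subject matter is bleeding risk. Navitoclax speeds the death of circulating platelets (Section 6.1.7.1). Thrombocytopenia was reported in 88% of the 34 subjects in Cohort 1a (Section 3.4), and hemorrhagic events are a safety topic of interest in SAP Appendix E. A list that sites are told to consult should not conditionally permit a platelet-inhibiting drug at a dose the criteria rule out.

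There may also be a reporting effect. SAP Appendix A counts subjects who took a prohibited concomitant medication, and a drug with two statuses could be classed either way. Neither document says which text drives that classification, so this is a possibility only.

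**Working it through.** No arithmetic applies. The check sets the statements side by side and asks which can stand together.

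| Place | Aspirin above 100 mg per day during treatment |
|---|---|
| Synopsis, key exclusions | Barred; exception stops at 100 mg per day |
| Section 5.2.2, criterion 3 | Barred; exception stops at 100 mg per day |
| Section 5.2.4, aspirin bullet | Not allowed; only 100 mg per day or less |
| Appendix H, anti-platelet list | Excluded |
| Appendix H, NSAID list with footnote | Cautionary; limited duration if platelets exceed 100 × 10⁹/L |

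1. **Same drug, same threshold.** Both Appendix H entries name aspirin and both start above 100 mg per day. Neither refers to indication or to length of use in the entry itself.
2. **Not an artefact of the text layout.** The NSAID column runs together with the CYP2C9-substrate column in the extracted text, but both headings are marked cautionary. The aspirin entry is cautionary whichever column it belongs to.
3. **Which entry is wrong.** Four of the five rows agree that the drug is barred, and three of those are the synopsis and the main-text rules. Only the cautionary entry departs from them.
4. **The NSAID bullet in Section 5.2.4.** It states the same platelet and duration condition as the footnote but does not mention aspirin. Aspirin has its own bullet in the same section, with a 100 mg cap, and the specific rule governs. The bullet is therefore not part of the conflict. The appendix is, because it names aspirin at the higher dose on the NSAID list.
5. **Extent of the conflict.** For use that is not of limited duration, or at platelets of 100 × 10⁹/L or below, the footnote gives no permission and the two entries agree in effect. They diverge only for short courses above 100 mg per day at counts above 100 × 10⁹/L. The route for medically indicated use in Section 5.2.4 applies equally to both statuses, so it does not alter the comparison.

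**The case against.** The best case against the point accepts the duplicate and disputes that it matters. Appendix H is only a sample list, and the main text settles the question at 100 mg per day. A cautionary listing is not free permission either: Section 5.2.4 sends the investigator to the sponsor's medical director for excluded and cautionary drugs alike. The two headings might also be read as separating antiplatelet use from short analgesic use. Criterion 3 is already qualified elsewhere, since Section 5.2.4 allows NSAIDs as a class for limited periods, and no precedence rule is written down. Calling the cautionary entry the wrong one is then an inference.

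Part of this stands. The shared notification step reduces the practical risk, and the deviation effect is unproven. Section 5.6.3 also describes dose escalation in Cohort 1a as generally free of clinically relevant bleeding related to thrombocytopenia.

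The rest does not remove the conflict. A sample list may omit drugs, but that does not explain opposite statuses for a drug it includes. The notification clause covers both classes and so does not say which applies. The split between antiplatelet and analgesic use appears nowhere in the text: both entries are defined by daily dose, and neither criterion 3 nor the aspirin bullet makes an exception by indication. If the NSAID reading were adopted anyway, the excluded entry would become the wrong one, and Appendix H would still contradict itself.

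**Conclusion.** The point holds. Appendix H contradicts itself on aspirin above 100 mg per day, and the cautionary entry is the one at odds with the synopsis, criterion 3 and the aspirin bullet in Section 5.2.4. That conclusion rests on reading the specific aspirin cap as governing over the general NSAID allowance. The documents do not state this precedence, but every main-text statement that names aspirin supports it.

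The matter is minor: a correction worth making, with no bearing on the trial's conclusions. It is confined to short courses at platelets above 100 × 10⁹/L, and the number of subjects cannot be estimated because aspirin use is not reported. The sample size, the primary endpoint and the analysis sets are unaffected. The status of the other NSAIDs on the list is a separate question and is not judged here.

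**What to change.** Delete the aspirin line from the cautionary NSAID list in Appendix H, leaving aspirin above 100 mg per day with the single status of excluded, as in criterion 3.

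As an optional clarification, add an exception for aspirin above 100 mg per day to the Appendix H NSAID footnote and to the NSAID bullet in Section 5.2.4. This is not needed to resolve the conflict, since the aspirin bullet already governs, but it would spare sites from having to infer it.

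The cost is one deleted line at the next amendment.

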Appendix I. Dose Adjustment Guidelines for Thrombocytopenia and Neutropenia

- After navitoclax and/or ruxolitinib dose modification, platelet counts should be rechecked approximately 7 days or sooner as clinically applicable until at least 2 consecutive laboratory values indicate stable platelet count.
- If treatment is interrupted, recheck platelets approximately every 2 to 3 days until recovery of platelets to $\geq 50 \times 10^9/L$.
- Navitoclax Dose levels for daily dosing: 200 mg, 150 mg, 100 mg, 75 mg or 50 mg

Hematology Results	Action For Navitoclax	Navitoclax (All Cohorts)	Ruxolitinib Per Approved Local Label (Cohorts 1a, 1b, and 3)			
	Dose Modification for Thrombocytopenia					
Platelet counts ≥ 75 × 10 ⁹ /L	No change OR Increase dose	 Maintain current dose if platelet count ≤ 100× 10⁹/L Dose may be increased to 150 mg if the current dose of navitoclax is 100 mg and administered for at least 7 days and platelets have increased to > 100 × 10⁹/L. Dose may be increased to 200 mg if the current dose of navitoclax is 150 mg and administered for at least 7 days and platelets have increased to > 150 × 10⁹/L. 	 Reduce dose if current dose > 10 mg twice daily Maintain current dose if receiving 10 mg twice daily Dose may be increased to the label recommended dose if the current dose is lower than the label recommended dose and current dose of ruxolitinib has been administered for at least 7 days and platelet counts have remained stable at > 125 × 109/L with no other dose modifications of the regimen 			
Platelet counts ≥ 50 × 10 ⁹ /L to < 75 × 10 ⁹ /L	Dose reduction OR No Change	 Reduce navitoclax dose if platelets do not return to ≥ 75 × 10⁹/L OR Maintain current dose if counts are stable and no risk for bleeding per investigator discretion 	Consider dose reduction.			

EudraCT 2017-001398-17

- After navitoclax and/or ruxolitinib dose modification, platelet counts should be rechecked approximately 7 days or sooner as clinically applicable until at least 2 consecutive laboratory values indicate stable platelet count.
- If treatment is interrupted, recheck platelets approximately every 2 to 3 days until recovery of platelets to $\geq 50 \times 10^9/L$.
- Navitoclax Dose levels for daily dosing: 200 mg, 150 mg, 100 mg, 75 mg or 50 mg

Hematology Results	Action For Navitoclax	Navitoclax (All Cohorts)	Ruxolitinib Per Approved Local Label (Cohorts 1a, 1b, and 3)		
	Dose Modification for Thrombocytopenia				
Platelet counts < 50 × 10 ⁹ /L	Dose interruption	• Resume at one dose level lower than prior to interruption once platelet counts recover to $\geq 50 \times 10^9/L$	Interrupt per local label. May taper if high risk for exacerbation in discussion with TA MD.		
			• Resume per local approved label guidance once platelet counts recover $\geq 50 \times 10^9/L$		
Dose Modification for Neutropenia					
Absolute neutrophil count (ANC)	Dose interruption	• Monitor hematology labs at least weekly until ANC \geq 1.0 \times 10 ⁹ /L	Maintain current dose or interrupt if at risk for infection per investigator		
$< 1.0 \times 10^9/L$ to $0.5 \times 10^9/L$		• Resume at one dose level lower once ANC recover $\geq 1.0 \times 10^9/L$	discretion.		
Absolute neutrophil count (ANC) < 0.5 × 10 ⁹ /L	Dose interruption	 Monitor hematology labs at least weekly or often as needed until ANC ≥ 1.0 × 10⁹/L. Resume at one dose level lower once ANC recover ≥ 1.0× 	May interrupt per local label. May taper if high risk for exacerbation in discussion with TA MD.		
		10 ⁹ /L	• Resume at same or lower dose.
